#### 10.B. Aim 2 Analysis Plan.

We will compare adoption, implementation, maintenance, and reach over time and between care models using both quantitative and qualitative data collected throughout the intervention period. A “Learning Evaluation” approach includes gathering data describing changes and how they are implemented, collecting relevant process and outcome data, assessing multi-level contextual factors affecting implementation, supporting sites in using the data to make improvements, and developing sustainable measurement strategies. Under the guidance of [name], our study will collect data relevant to each component of a Learning Evaluation, and we will use a mixed-methods presentation of our data to provide real-time monitoring and feedback to stakeholders to support intervention fidelity and a summary assessment of how fully each care model was implemented. The modality to achieve a systematic and responsive evaluation will be “joint reports” organized by components of the RE-AIM framework (adoption, implementation, maintenance and reach), produced and distributed monthly over 24 months. Summary level data describing care

processes, care outcomes, changes, and contextual factors will be presented in aggregate and by study site. The integrated reports will include interpretation and recommendations from our team to each clinic to support development of a successful care model, and will be disseminated to stakeholders in webinars and written form. Stakeholder feedback will be collected and interpretations adjusted accordingly. Over time, these reports will present a historical record of summary-level data, key events and adaptations, recommendations, and assessments of success to describe the implementation process and provide sites with a methodological framework to continue improvement in BP care in the future.

Adoption will be described by clinic characteristics (e.g. geographic region, size, patient mix, pre-implementation performance metrics), field observation notes (clinic site visits, meeting minutes, and notes on organizational context) and interviews with clinicians and clinic leaders about barriers to adoption and willingness to be randomized.

Implementation and Maintenance will be described by metrics representing elements of the care approach to which clinics have been assigned. Implementation fidelity is expected to be similar for some (eg, BP accuracy, free BP checks, repeat elevated BP, re-assessed elevated BP, registry use) while others may be more frequent in one group (clinic-based or telehealth). Field observation notes (site visits, chart audits), interviews with clinicians, and patient focus groups will provide insights into differences in the metrics, but also perspectives at the clinic and organizational level about the implementation and maintenance process itself (eg, barriers or disagreement with the care process, factors promoting success, adaptations to clinicians protocols, and description of the care patients report receiving). We will produce key aggregate summaries of these data at 12 months (Implementation) and 24 months (Maintenance), along with statistical comparison between groups with 95% CIs.

Reach will be quantified as the proportion and 95% CI of eligible patients who pass through each step of engagement in their clinic's care approach: attend BP check, have uncontrolled BP, follow up with PCP (clinic based) or pharmacist/NP (telehealth). We expect similar proportions of patients in each care approach to meet these criteria both monthly and in aggregate over 24 months. We will examine eligible patient characteristics for evidence of disparities in Reach, and field observations, interviews, and patient focus groups will be examined for barriers to engagement, reasons for any disparity in engagement, and potential solutions.

By the end of the study period, we will have accrued 24 months of integrated data reports that we will use to construct recommendations to clinics to continue improvement in BP care. Our final report will include data stratified and summarized on several dimensions describing key events over the course of implementation: context (time and setting), approach to care models by clinics and clinicians, patient experiences, barriers, objections, and factors promoting success. These data will be used to compare how fully each care model was implemented and to recommend strategies for clinics to monitor their own progress in improving BP care in the future using standardized reports.

#### **10.C. Reporting Plan (IR-6).**

Reports of the trial design and outcomes will include sufficient information to allow assessments of the study's internal and external validity. The external validity can be assessed in part by conformity to PRECIS2 criteria, including broad eligibility criteria, a real-world health care system setting, enrollment and flexible interventions carried out by clinical staff, and follow up conducted without additional research visits. Reports of the trial outcome will conform to the CONSORT guidelines, including the extensions for patient-reported outcomes and cluster-randomized trials.

#### **11. Data Management**

The overwhelming majority of data used to assess implementation and test the Aim 1 and 2 hypotheses are derived from electronic sources whose primary function is to deliver and document care delivered in a health care setting. Clinic staff update missing or invalid values as needed at each clinic encounter. Fields used to characterize patients included in the preliminary analyses were virtually 100% populated, with race being the most frequently missing (4%).

EHR-based data are identified by encounter- and patient-specific (ie, medical record number, MRN) identifiers that link information across tables. The study programmer will maintain a crosswalk that associates each MRN with a HIPAA-compliant random identifier that uniquely identifies patients in the analytic datasets and survey sampling frames.

## **12. Key Milestones and Timeline**

Below are dates for key study activities. See Appendices J, K and L for full timeline, enrollment timeline, and milestones as reported to PCORI.

### **12.A. Study Start-up**

- Jan 1, 2017: Protocol and research application completed, submitted to IRB
- March 1, 2017: IRB approved study protocol
- Jan-Feb 2017: AMC vendor testing and Epic vitals flowsheet development
- May 2017: Pilot test patient survey

### **12.B. Enrollment and Interventions**

- May-July 2017: Recruitment and training of clinics (site visits to n=20 clinics)
- July 2017: First clinics “go live” with interventions as randomized for Vanguard Phase
- November 2017: Main Trial enrollment begins
- March 1, 2019: Patient enrollment complete
- March 1, 2021: Final Patient Surveys collected (24-months)
- “Implementation Phase” of Interventions (0-12 months): August 2017-July 2018
- “Maintenance Phase” of Interventions (12-24 months): August 2018-July 2019
- Evaluation Reports to clinics: Monthly, September 2017-August 2019

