## **15. Data and Safety Monitoring Plan – Approved by DSMB April 17, 2017**

### **Plan for monitoring study conduct and safety**

#### **1. Clinic recruitment, randomization and characteristics of clinics**

**1.1 Clinic recruitment.** Clinics will be eligible to participate if they have a Medication Therapy Management (MTM) pharmacist onsite at least one half-day per week and use standardized methods to measure BP with validated oscillometric BP monitors. Eligible clinics will be contacted via their leadership and invited to participate if they are willing to be randomly assigned to clinic-based care or telehealth care, participate in training, participate in limited data collection activities, and receive periodic feedback on implementation of the elements of clinic-based care or telehealth care according to their randomized assignment.

Twenty eligible clinics will be identified for randomization into clinic-based or telehealth care. Four clinics will function as vanguard clinics. Study algorithms will be implemented in the electronic health record systems of these four clinics prior to August 1, 2017. Vanguard clinic staff will have two months to observe how the algorithms modify work flow and offer suggestions for improvement. The study team will incorporate changes as needed based on user feedback prior to implementing the algorithms in the remaining 16 clinics by November, 2017.

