**1.2 Cluster randomization.** Given the relatively limited number of randomization units, we wish to ensure that clinics are not imbalanced across treatment groups on factors related to the primary outcome, the ability to implement the intervention or potential treatment modifiers. Stratifying on clinic BP control should ensure that the treatment groups are similar with respect to the primary outcome (SBP) at the time the intervention is implemented. Clinic BP control is likely related to the how effectively clinical practices that support provision of recommended care are currently implemented, so that balance on clinic BP control may also balance factors related to the likelihood that the interventions will be implemented successfully. Clinic BP control is correlated with the proportion of clinic patients who are members of racial or ethnic minority groups, and with the proportion who have comorbid conditions that complicate hypertension treatment, so that balance on clinic BP control may also balance these potential treatment modifiers. An added practical consideration to incorporate into the randomization scheme is that the vanguard clinics must be split evenly between clinic-based care and telehealth care.

We plan to stratify the clinics first into the 4 vanguard and 16 main study clinics. Participants enrolled in the early Vanguard Phase of the study will not be included in the main trial results. Among the main study clinics we will create 2-4 more small strata of at least 4 clinics each based on the proportion of clinic patients on the hypertension registry whose SBP and DBP meet clinical recommendations for control in the month prior to randomization. The study statistician will assign the clinics within each stratum equally to clinic-based care or telehealth care based on values of randomly generated numbers. The main study clinics in clinic-based care and telehealth care (8 each) should be balanced on clinic BP control. However, the simple randomization of the 4 vanguard clinics may perturb the balance in clinic BP control that could otherwise be attained through stratified randomization of all 20 clinics. We acknowledge that some of the precision gained through stratified randomization may be lost but assert that the opportunity to fine tune the algorithms, work flow or user interface will strengthen the intervention sufficiently to counteract this loss.

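### The Aim 2 Implementation and Maintenance windows start in August 2017, but 16 of 20 clinics go live only by November 2017, so in those clinics they end at about 9 and 21 months of exposure

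*Combined protocol and SAP*

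**What the plan says.** Section 12.B lists the Implementation Phase as "of Interventions (0-12 months): August 2017-July 2018" and the Maintenance Phase as "of Interventions (12-24 months): August 2018-July 2019". The same list gives "Evaluation Reports to clinics: Monthly, September 2017-August 2019".

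Section 10.B attaches the Aim 2 summaries to these labels: "We will produce key aggregate summaries of these data at 12 months (Implementation) and 24 months (Maintenance"), together with statistical comparisons between groups and 95% CIs.

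Section 15 describes a staggered start. Item 1.1 says of the vanguard clinics: "Study algorithms will be implemented in the electronic health record systems of these four clinics prior to August 1, 2017". It adds that "Vanguard clinic staff will have two months to observe how the algorithms modify work flow", and that changes are made "prior to implementing the algorithms in the remaining 16 clinics by November, 2017". Item 2.2 starts enrollment in the vanguard clinics in August 2017 and in all 20 clinics in November 2017; section 12.B also puts the start of main trial enrollment in November 2017. Item 1.2 states: "Participants enrolled in the early Vanguard Phase of the study will not be included in the main trial results".

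Nothing in the available text ties month 0 to a clinic's own go-live or removes the months before it.

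**The concern.** The phase labels describe time since the intervention began, while the dates attached to them describe time since the vanguard start. The two agree for the four vanguard clinics but not for the other 16.

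Maintenance is a named Aim 2 objective, and section 10.B promises summaries at 12 and 24 months. If the printed dates are followed, the Implementation summary can include months in which most clinics had no study algorithms, and the Maintenance summary includes months that are still part of those clinics' first year. A measure that rises after go-live could then appear to improve between phases simply because its early months came before the start. The 24-month label would also be attached to about 21 months of exposure in 80% of clinics (16/20).

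**Working it through.** **Inputs.** Phase windows and report dates come from section 12.B. Clinic numbers and go-live dates come from section 15, items 1.1 and 2.2: 4 clinics before 1 August 2017 and 16 by November 2017. Two further values give a range. October 2017 is an assumed earliest roll-out, from the two-month vanguard observation period. Two vanguard clinics is the lower figure in section 4.D, which allows 2 to 4. Months are counted inclusively, with go-live at the start of the month.

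**1. The plan's own lengths.** August 2017 to July 2018 is 5 + 7 = 12 months. August 2018 to July 2019 is 12 months. Reports from September 2017 to August 2019 number 4 + 12 + 8 = 24. The labels are therefore consistent with an August 2017 start.

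**2. Implementation window.** Clinic-months before go-live = (clinics not yet live) × (months before go-live), out of 20 × 12 = 240.

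| Vanguard clinics | Roll-out to the rest | Clinic-months before go-live | Share of 240 | Months of exposure by July 2018 / July 2019 |
|---|---|---|---|---|
| 4 | November 2017 | 16 × 3 = 48 | 20% | 9 / 21 |
| 4 | October 2017 | 16 × 2 = 32 | 13.3% | 10 / 22 |
| 2 | November 2017 | 18 × 3 = 54 | 22.5% | 9 / 21 |
| 2 | October 2017 | 18 × 2 = 36 | 15% | 10 / 22 |

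Within one of the 16 clinics, a November go-live leaves 3 of 12 months (25%) before the start.

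**3. Maintenance window.** For a November 2017 go-live, the first 12 months run to October 2018. August, September and October 2018 therefore belong to the first year: 16 × 3 = 48 of 240 clinic-months (20%). No month of this window precedes go-live.

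**4. Which measures are exposed.** Section 15, item 3.1 uses several denominators.
- *Telehealth delivery* is measured in enrolled patients of telehealth clinics. The 16 later clinics have none before go-live, so these measures are not diluted. Until roll-out they rest on vanguard clinics alone.
- *Hypertension care processes* use registry-eligible, Hyperlink-eligible or enrolled patients, and *Reach* (section 10.B) uses eligible patients. The first two denominators can exist before go-live. Section 10.A.3 shows this is practical, because patients meeting similar criteria in the randomized clinics were identified from 1 May 2017.
- *Infrastructure and policy elements* were already in place in all clinics (section 5.A.1), so the early months are not empty for them.

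**5. Size of the dilution.** Let f be the level of a measure after go-live and p its level before. With equal weight per clinic-month (an assumption; the plan sets no weighting) and 20% of months before go-live, Implementation would be reported as 0.8f + 0.2p and Maintenance as f. The spurious gain is 0.2(f − p). It is zero if p = f. The documents give neither f nor p, so no numerical bias follows.

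**The case against.** The strongest reply is that section 12.B is a milestone list, that section 10.B gives no calendar dates, and that the measure definitions and full timeline sit in Tables 2 and 3 and Appendices J to L, which are not in the available text. A clinic-specific clock may exist there. At least one Aim 2 maintenance item, the patient-reported outcome descriptives in Table 4 of section 15, uses surveys timed from patient enrollment rather than from August 2017. This limits certainty about how the windows would be applied. It does not remove the conflict between section 12.B and section 15.

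Several stronger readings are tempting, and the reply is right to resist them:
- *Maintenance also mixes in pre-intervention months.* It does not; see step 3.
- *A large false gain can be quantified.* Assuming 60% fidelity after go-live and 0% before would give 48% against 60%. The documents do not support 0%: infrastructure was in place, and section 6 plans training in all 20 clinics in June and July 2017. Telehealth delivery measures have no denominator before go-live in the 16 clinics.
- *The comparison between arms is biased.* Item 1.2 splits the vanguard clinics evenly between arms, and no arm difference in roll-out timing is stated.
- *Twenty-four-month maintenance cannot be known for 80% of clinics.* The 2019 dates are a reporting cutoff. Fidelity measures use mainly routine electronic data, and EHR observation runs to April 2021 (section 15, item 4.5), so later months could be extracted.
- *Vanguard months must be dropped from Aim 2.* Item 1.2 excludes vanguard participants from the main trial results and does not mention implementation data.

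It is also fair that monthly, site-level reporting would let a careful analyst separate the early months. The plan does not say that the 12- and 24-month aggregates will do so.

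**Conclusion.** The inconsistency is real and limited to Aim 2. As printed, 0-12 and 12-24 months mean about 0-9 and 9-21 months of exposure in 16 of 20 clinics. Up to 20% of Implementation clinic-months precede go-live; by November is a latest date, and the range is 13.3% to 22.5% depending on roll-out month and number of vanguard clinics. The consequence is a possible distortion of the change from implementation to maintenance for measures on registry-eligible or Hyperlink-eligible denominators, of a size the documents do not determine. Telehealth delivery measures are undiluted but come from vanguard clinics alone until roll-out. H1.1 and H1.2 are timed from each patient's enrollment (section 10.A) and are unaffected. The conclusion assumes that the section 12.B dates govern the section 10.B summaries and that no clinic-specific clock is set in the unavailable tables and appendices.

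**What to change.** Reconcile section 12.B with section 15, items 1.1 and 2.2. In sections 12.B and 10.B, define month 0 as each clinic's go-live date, Implementation as months 0-12 and Maintenance as months 12-24 from that date. For the 16 later clinics this gives about November 2017 to October 2018 and November 2018 to October 2019. Report the vanguard tuning months separately. Run the monthly extracts and the final summary through about October 2019. If Tables 2 and 3 or Appendices J to L already use a clinic-specific clock, align section 12.B with it.

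The cost is protocol wording, about three more routine EHR extracts, and a maintenance summary issued about three months later. No patient contact is needed.

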### **12.C. Key reporting milestones**

- Reporting Periods for Interim reports to PCORI: January 1 and July 1 annually, 2017-2021
- DSMB Meetings: Twice annually, August and February 2017-2021
- Patient Advisory and Stakeholder Advisory Board Meetings: Once/quarter, April, July, October and January 2017-2021.

### **12.D. Publication and Dissemination**

See below section 16 for details on milestones related to publication and dissemination.

### 13. Organization

This study represents a unique collaboration between research organizations, care systems, patient co-investigators and advisors, and other interested stakeholders. The study teams are organized to draw on strengths of all collaborators. Collaborators include:

- HealthPartners Institute
- HealthPartners Medical Group, Health Plan, and Pharmacy Departments
- Patient Investigators
- Patient Advisors (from HealthPartners and nationally via Health eHeart Alliance)
- University of California San Francisco and Health eHeart Alliance
- Researchers from Group Health Institute, Robert Wood Johnson Medical School, University of Mississippi Medical Center
- Professional representatives from American Society of Hypertension, AMC Health, American Medical Association, American Heart Association

Team members and stakeholders will be arranged around a core team with smaller topic sub-groups that will shift according to the study's needs, and additionally a Patient Advisory Board and Stakeholder Advisory Board that will each have some cross-over with the study team. See Appendix I for an org chart of the study team. Scopes of work are described below.

#### 13A. Steering Committee/Core Team.

The Steering Committee will consist of the Principal Investigator, co-investigators, representatives from each subcommittees, and project managers. This group will lead the direction of the study and have leaders of each of the below workgroups represented in most research team meetings. Core team meetings occur weekly.

**13.A.1. Clinic Operations workgroup.** The Clinic Operations Team will co-develop the intervention workflows for patients with hypertension and develop an implementation plan for the two interventions. This team will also review clinic performance over time and offer recommendations to the research team about how to best support intervention success in the clinics.

**13.A.2 Technology and Informatics workgroup.** This team will identify device vendors and develop infrastructure for BP telemonitoring and home BP monitoring data transfer into Epic. This team will also design electronic tools to track patient data and ensure consistent intervention processes. The team will work closely with HP to test and gain approval for use of systems and tools developed for the study.

**13.A.3. Measurement and analysis workgroup.** The Measurement and Analysis Team will develop and refine measures to successfully carry out Aims 1 and 2. Measures will include EHR and claims electronic data, patient-reported data collected by surveys, and qualitative data collected by focus groups and field observations. This team will also be responsible for developing monitoring reports to clinical partners to support intervention fidelity and assess intervention implementation using the RE-AIM model.

**13.A.4. Engagement workgroup.** The Engagement Team will work to determine the best ways to engage patients and other stakeholders including those on the Patient and Stakeholder Advisory Boards and other stakeholders in order to ensure full implementation of the interventions and clear dissemination of results.

### **13.B. Patient Advisory Board**

The PAB consists of two patient investigators and 6-9 patient advisors from HealthPartners and Health eHeart Alliance (administered at University of California at San Francisco). The Health eHeart Alliance will facilitate the convening of the study PAB and ongoing meetings. Over the course of the project, the PAB will advise the research team about the patient perspective on all aspects of the study including: implementation, communication strategies and reporting of results.

Specific key goals for the PAB include: advising on patient reported outcomes, vetting and testing the patient survey, advising on communication with patients about the interventions, reviewing interim results and identifying opportunities for maximizing the interventions' "reach" and success in engaging a wide diversity of patients. The PAB will advise the study team on disseminating results to a wide variety of organizations and stakeholders, especially patients.

Meetings will take place by teleconference at quarterly intervals following a series of introductory teleconferences. There will also be one in-person meeting before the interventions begin for the PAB to give concentrated input on the study intervention design. PAB members will be compensated at a rate of \$50/hour for each hour of meeting time. Payments will be disbursed twice per year from Health eHeart.

